5.7.2.4 Clinical Impression of Severity Index – PD

The CIS-IPD is a severity index formed by four items (motor signs, disability, motor complications, and cognitive status), rated 0 (not at all) to 6 (very severe or completely disabled) (Martinez-Martin, 2006). A total score is calculated by summing the item scores.

The CISI-PD is administered in the on-medication state at Baseline, and Weeks 2, 4, 8, 12, and 14. The total score will be summarized

descriptively at each scheduled visit. To evaluate change from baseline in the total score, the same MMRM model used to evaluate the primary endpoint will be employed to produce LS means, SE, and 95% CIs of the LS means for each treatment arm at each scheduled visit. The unadjusted mean change from baseline, and the difference in LS means between treatment arms and 95% CI of the difference will also be calculated. A summary of each parameter will be presented as well.

5.7.2.5 PD Quality of Life Questionnaire-39

The PDQ-39 is a self-administered questionnaire of 39 questions relating to 8 key areas of health and daily activities, including both motor and non-motor symptoms (Peto, 1998). The eight dimensions include: mobility, activities of daily living, emotional well-being, stigma, social support, cognition, communication, and bodily discomfort. It is scored on a scale of 0-100 with lower scores indicating better health and high scores indicating more severe symptoms.

The PDQ-39 is collected at Baseline and Weeks 2, 4, 8, 12, and 14. The total scores for each of the eight dimensions and the overall total score will be summarized descriptively at each scheduled visit. To evaluate change from baseline, the same MMRM model used to evaluate the primary endpoint will be employed to produce LS means, SE, and 95% CIs of the LS means for each treatment arm at each scheduled visit. The unadjusted mean change from baseline, and the difference in LS means between treatment arms and 95% CI of the difference will also be calculated.

5.7.2.6 Sheehan-Suicidality Tracking Scale

The S-STS was developed to provide a brief but efficient instrument for use in assessing change in suicidal ideation and behavior while providing a comprehensive description of suicidal ideation and behavior (Sheehan, 2014). The standard version of the S-STS is a 16-item scale that assesses the seriousness of suicidality phenomena on a Likert-type scale (0-4) ranging from “not at all” (0) to “extremely” (4). It also assesses the frequency of key phenomena and the overall time spent in suicidality.

The S-STS is collected at Baseline and Week 12. Total score will be summarized descriptively at each scheduled time point. To evaluate change from baseline, an analysis of covariance (ANCOVA) model will be used to produce the LS mean, SE, and 95% CI of the LS means for each treatment arm. The unadjusted mean change from baseline, and the difference in LS means between treatment arms and 95% CI of the difference will also be calculated.

5.7.2.7 10-Meter Timed Walk

The 10-meter walk test is a commonly used tool for assessing gait speed in individuals with gait limitations (Lang, 2016). Gait speed is positively correlated with the amount of community ambulation and quality of life, and it is an important measure of mobility in individuals with PD.

The 10-meter timed walk is conducted in the on-medication state at Baseline and Weeks 2, 4, 8, 12, and 14, as well as the off-medication state at Baseline and Weeks 4, 12, and 14. Based on two consecutive measurements, average comfortable walking speed (CWS) (m/s) and fast walking speed (FWS)(m/s) will be calculated for each subject at each scheduled visit. CWS and FWS will then be summarized descriptively at each scheduled visit by treatment arm. The difference in both the CWS and FWS between the on-medication and off-medication state will also be reported.

To evaluate change from baseline, the same MMRM model used to evaluate the primary endpoint will be employed to produce LS means, SE, and 95% CIs of the LS means for each treatment arm at each scheduled visit. The unadjusted mean change from baseline, and the difference in LS means between treatment arms and 95% CI of the difference will also be calculated.

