5.2.2 Modified Intention-to-Treat (mITT)/Evaluable Population

The mITT/evaluable population will be a subset of the ITT population that only includes subjects with non-missing baseline and Week 12 (Day 84) values for off-medication motor function as measured by the MDS-UPDRS Part 3. Analysis will be done according to the treatment subjects were randomized to.

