5.7 Efficacy Analyses

Efficacy analyses will evaluate the effects of AKST4290 on motor function in the off-medication state, as well as the potential effects on clinical function and activities of daily living. Efficacy endpoints will be evaluated using the mITT/Evaluable and PP populations.

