5.7.2 Secondary Efficacy Endpoints

Secondary efficacy endpoints will be analyzed using the mITT/Evaluable, ITT, and PP populations. Please see Safety Analysis section (Section 5.8) for information regarding analysis of safety endpoints.

Secondary efficacy endpoints include the following:

Change from Baseline (Day 1) in clinical function, motor function, and activities of daily living at Week 12 (Day 84) during the on-medication state as assessed by:

- MDS-UPDRS Parts 1-4
- Montreal Cognitive Assessment
- Schwab and England Activities of Daily Living Scale
- Clinical Impression of Severity Index – PD
- PD Quality of Life Questionnaire-39
- Sheehan-Suicidality Tracking Scale
- 10-meter timed walk (will also be assessed in the off-medication state)
- Hauser 3-Day Patient Diary

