5.8 Safety Analyses

Safety analysis includes study drug accountability, incidence and severity of treatment emergent adverse events, laboratory parameters, vital signs, 12-lead ECG, physical examination, pregnancy tests, and prior and concomitant medications. Unless otherwise specified, safety parameters will be summarized by treatment group using the safety population.

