5.8.9 Prior and Concomitant Medications

The number and percentage of subjects taking any prior and concomitant medications will be summarized by anatomical therapeutic chemical (ATC) level 3 terms and preferred medication names.

FM DM015.1
Statistical Analysis Plan
AKST4290-211

Rev B
Page 27 of 30

6 Document Version Control

Revision History:

REVISION	RELEASE DATE	AUTHOR	SUMMARY OF CHANGES
A	23Dec2020	[name]	Original release
B	08Apr2021	[name]/[name]	-Modify specification of MMRM model to ANCOVA model, when only baseline and Week 12 data. -Per Sponsor request add ITT population for efficacy tables; add breakdown of each cognitive domain for MoCA, include mean scores for SE-ADL; add breakdown of each parameter for CISI-PD; include overall summaries for abnormal Chemistry lab summary table. -Other minor edits

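### The S-STS is planned only as an efficacy mean change: no Safety-population count of emergent suicidality, and no rule for early-termination scores

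*SAP*

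**What the plan says.** Section 5.7.2.6 describes the S-STS as a measure of suicidal ideation and behaviour. On timing it says "The S-STS is collected at Baseline and Week 12". Two outputs are planned. The first is descriptive: "Total score will be summarized descriptively at each scheduled time point". The second is a comparison of change from baseline, for which "an analysis of covariance (ANCOVA) model will be used to produce the LS mean, SE, and 95% CI of the LS means", together with unadjusted mean change and the difference between arms with its 95% CI.

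Sections 3.2 and 5.7.2 list the scale with the change-from-baseline secondary endpoints. For these, Section 5.7.2 says "Secondary efficacy endpoints will be analyzed using the mITT/Evaluable, ITT, and PP populations". The general statement in Section 5.7 is narrower: "Efficacy endpoints will be evaluated using the mITT/Evaluable and PP populations". The Revision B entry in Section 6 records the addition of ITT: "Per Sponsor request add ITT population for efficacy tables".

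The mITT set (Section 5.2.2) "only includes subjects with non-missing baseline and Week 12 (Day 84) values for off-medication motor function". The PP set (Section 5.2.4) also needs complete baseline and Week 12 assessments. Section 5.6 limits imputation to the primary endpoint.

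Section 5.8 opens: "Safety analysis includes study drug accountability, incidence and severity of treatment emergent adverse events, laboratory parameters, vital signs, 12-lead ECG". The list continues with physical examination, pregnancy tests and medications. The S-STS is not in it.

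**The concern.** Suicidality is a question about individual subjects: did anyone develop or worsen in ideation or behaviour, and in which arm? The planned S-STS output answers a different question, namely whether the average total score moved.

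Three features combine. First, because the scale is classed as efficacy, the rule in Section 5.2.3 that safety endpoints are summarised in the Safety population by treatment received does not reach it. Second, no output from the instrument is a count of subjects. Third, the subjects most relevant to a suicidality question may be those who stop early, and the plan does not settle whether their S-STS scores enter any table. With only two scheduled assessments, an early-termination score may be such a subject's only post-baseline value.

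At stake is whether the S-STS tables can be relied on to show an imbalance between arms if there is one.

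**Working it through.** **Plan figures.** The SAP gives no expected rate, SD or target for the S-STS, so there is no planned result to reproduce. The one relevant figure is in Section 4.4: about 120 randomised 1:1 to obtain about 108 evaluable. This implies 120 - 108 = 12 subjects (12/120 = 10%), about 6 per arm, outside mITT.

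**Who contributes an S-STS change score.**
- mITT: membership depends on baseline and Week 12 off-medication Part 3, a motor score unrelated to suicidality. A subject without that Week 12 score is excluded whatever the S-STS shows.
- PP: complete Week 12 assessments are required, so early stoppers are again out unless an early-termination visit is treated as Week 12.
- ITT: all randomised subjects belong (Section 5.2.1). An ANCOVA of change to Week 12 still needs a Week 12 value, and Section 5.6 provides no imputation here, so a subject without one adds nothing.
- Early termination: Section 4.7 asks sites to attempt the Visit 6/EOT assessments, which include the S-STS in the Section 4.8 schedule. It lists early termination separately and analyses visits as nominal. No rule assigns the early-termination score to Week 12, and none excludes it.

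**Sensitivity of a mean to a few cases (assumed numbers).** Take 60 per arm. On active, 3 subjects go from 0 to 10 and 57 stay at 0. On placebo, all 60 stay at 0.
- Difference in means = 30/60 - 0 = 0.50.
- Active-arm variance = (3 × 10² - 60 × 0.50²)/59 = (300 - 15)/59 = 4.83. Placebo variance = 0.
- SE = √(4.83/60) = 0.284.
- 95% CI = 0.50 ± 1.96 × 0.284 = -0.06 to 1.06, which includes zero.
- The descriptive table would show a maximum of 10 against 0, provided the scores are tabulated.

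**Possible loss outside mITT (assumed rates).** If each of the 12 subjects has probability p of emergent suicidality, the chance that at least one case lies outside mITT is 1 - (1 - p)^12:
- p = 2%: 1 - 0.98^12 = 22%
- p = 5%: 1 - 0.95^12 = 46%
- p = 10%: 1 - 0.90^12 = 72%

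Similarly, if an arm has 3 cases in 60 (5.0%) and 2 are in subjects outside mITT, the 54 evaluable subjects (108/2) show 1/54 = 1.9%.

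No figure in the last two blocks, other than the sample sizes, comes from the SAP.

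**The case against.** A reader might infer that the S-STS is analysed only in completers and that cases in early stoppers disappear from the trial's results. The SAP does not support that, for four reasons.

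- Section 5.7.2 names ITT, and the revision history shows it was added deliberately.
- An early-termination S-STS is to be attempted. The schedule labels the visit 6/EOT, so the score might be stored there and enter the ITT model. With an off-medication Part 3 score at the same visit, the subject could even qualify for mITT. The gap is an unstated rule, not a stated exclusion.
- Section 5.1 defines descriptive summaries to include the range, so an extreme tabulated score would be visible. It would be wrong to say the S-STS summary cannot show a case.
- Suicidality reported as an AE would be tabulated by SOC and PT in the Safety population, with severity, seriousness and AEs leading to discontinuation (Sections 5.8.2 to 5.8.2.2). Withdrawal reasons are summarised (Section 5.3), and Section 5.1 provides listings of all collected data. Parts of the AE section are blacked out, so whether suicidality is handled there as an event of special interest cannot be judged.

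It can also be said that the endpoint's classification may come from the protocol, which is not shown, so removing it from the secondary efficacy endpoints might need more than a SAP edit.

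All of this stands, and it limits the point. It does not supply a by-arm count, by treatment received, from the instrument collected to measure suicidality. AE reporting depends on a case being recorded as an event, a listing is not a comparison, and the range helps only if the score reaches the table.

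**Conclusion.** The point holds in a limited form. The S-STS is summarised and modelled only as an efficacy total score. No Safety-population or categorical summary of emergent or worsened suicidality is planned. Because imputation is confined to the primary endpoint and the use of early-termination scores is not defined, cases in early stoppers may be absent from the S-STS tables. Sections 5.7 and 5.7.2 also disagree on whether ITT applies.

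The size cannot be fixed from the document. About 12 of 120 subjects are expected outside mITT. The confidence interval and the 22% to 72% range rest on assumed case numbers and rates, and show only that a handful of cases can be missed or left unclear by a mean change. The weakness lies in the S-STS analysis, not in the whole safety plan. It is a worthwhile, cheap improvement and does not touch the primary analysis.

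**What to change.** Keep the S-STS mean change as listed among the secondary endpoints. Then:

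1. Add to Section 5.8 an S-STS table in the Safety population, by treatment received. Give n (%) of subjects with any post-baseline increase in total score, and n (%) with any ideation or behaviour item above its own baseline value.
2. Base that table on all post-baseline assessments, early termination included, and add a shift table from baseline to worst post-baseline value. State how many subjects have no post-baseline S-STS.
3. State in Section 4.7 or 5.7.2.6 whether an early-termination S-STS is treated as Week 12 in the ANCOVA.
4. Reconcile Sections 5.7 and 5.7.2 on the use of ITT.

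The cost is a few sentences of SAP text and one or two tables programmed from data already collected. The listing needs no addition, since Section 5.1 already provides for it. Because the mean change stays where it is, the endpoint list does not change.

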5.7.2.8 Hauser 3-Day Patient Diary

The Hauser Patient Diary was developed to assess functional status over a period of time in patients with motor fluctuations and dyskinesia (Hauser, 2000). It is a self-completed reference diary designed to separate dyskinesia that had a negative impact on patient-defined functional status from dyskinesia that did not. With this diary, the effect of an intervention can be expressed as the change in off-medication time and the change in on-medication time with troublesome dyskinesia (bad time). The sum can be used as an outcome variable and compared to baseline or across groups.

The Hauser 3-day patient diary is collected at Baseline and Week 12. Mean “bad time” (in hours) over the three days of collection will be summarized descriptively at both time points. Based on the research conducted by Hauser (2000, 2004), bad time is defined as the sum of off time and on time with troublesome dyskinesia. Mean “good time”, defined as on time without dyskinesia plus on time with non-troublesome dyskinesia, will also be summarized descriptively. Additionally, mean % day spent in “bad time” and “good time” will be summarized descriptively. Mean % day spent in “bad time” or “good time” is the mean number of hours spent in bad time or good time, divided by the mean number of waking hours over the three-day period.

To evaluate change from baseline in bad time, good time, mean % day spent in bad time, and mean % day spent in good time, an analysis of covariance (ANCOVA) model will be used to produce the LS mean, SE, and 95% CI of the LS means for each treatment arm. The unadjusted mean change from baseline, and the difference in LS means between treatment arms and 95% CI of the difference will also be calculated.

5.7.3 Exploratory Endpoints

Exploratory endpoints will be analyzed using the mITT/Evaluable populations. Only descriptive statistics will be provided, treatment comparisons will not be performed.

Exploratory endpoints included in this SAP are:

- Changes in concentration of AKST4290 and its major metabolites in plasma at various time points.
- Changes in bradykinesia, tremor, general activity, and sleep as measured by an FDA-cleared wearable sensor device.

Analysis of other exploratory endpoints may be performed, and are outside the scope of this SAP.

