5.2.3 Safety Evaluable Population

The safety population will consist of all subjects who received at least one dose of the study medication. All safety endpoints will be summarized for the safety population. Analysis will be done according to the actual treatment subjects received.

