5.7.3.1 Pharmacokinetics

Plasma concentration measurements of AKST4290 and the major metabolites M227 and M373 will be collected to assess systemic exposure to the study agent. Pharmacokinetic samples will be collected immediately prior (-15 min) to study drug administration at Baseline and Weeks 2, 4, 8, 12, and 14, as well as 1 hour and 2 hours after administration at Baseline and Weeks 4 and 12. A final PK sample will be collected at Follow-Up (Week 14). Concentration of AKST4290 in plasma will be summarized descriptively at each visit timepoint.

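### PK summary tables are limited to subjects with a Week 12 off-state motor score, grouped as randomised; the PK section also names only the parent drug and a pre-dose sample at Week 14

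*SAP*

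**What the plan says.** Section 5.7.3 covers all exploratory endpoints with one population rule: "Exploratory endpoints will be analyzed using the mITT/Evaluable populations". The analysis is descriptive: "Only descriptive statistics will be provided, treatment comparisons will not be performed".

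Section 5.2.2 says this set "only includes subjects with non-missing baseline and Week 12 (Day 84) values for off-medication motor function as measured by the MDS-UPDRS Part 3", and adds: "Analysis will be done according to the treatment subjects were randomized to". Section 5.2 defines no PK population, and section 5.7.3.1 does not override the rule.

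The contrast is section 5.2.3: "The safety population will consist of all subjects who received at least one dose of the study medication", with the grouping rule "Analysis will be done according to the actual treatment subjects received".

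On analytes, section 5.7.3 lists as an endpoint within the SAP's scope: "Changes in concentration of AKST4290 and its major metabolites in plasma at various time points". Section 5.7.3.1 says that AKST4290, M227 and M373 are all measured, to assess systemic exposure. Its one summary sentence reads: "Concentration of AKST4290 in plasma will be summarized descriptively at each visit timepoint".

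On timing, section 5.7.3.1 includes Week 14 in its list of samples taken 15 minutes before dosing, then describes a final sample at the Week 14 follow-up. In section 4.8, the schedule shows study agent administration at Visits 2 to 6 only, and note 5 places the pre-dose draw at Visits 2 to 6.

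**The concern.** Whether a plasma concentration is valid depends on what the subject took, when the sample was drawn and how it was assayed. It does not depend on whether a motor rating was obtained weeks later. Under the stated rule, a subject dosed and sampled at Baseline, Week 2, Week 4 or Week 8 who has no Week 12 off-state score drops out of the PK tables at those visits too. A subject still on drug with a good Week 12 sample also drops out if the off-state rating was missed. Section 4.8 note a expressly allows missed assessments to reduce COVID-19 exposure.

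Grouping as randomised protects a between-arm comparison, but section 5.7.3 says none will be made. For an exposure summary, it would place any misallocated subject's concentrations under a treatment that the subject did not take.

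At stake is how well the tables describe exposure among those dosed, whether a programmer working from 5.7.3.1 builds metabolite tables at all, and whether an off-drug value is labelled as pre-dose.

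**Working it through.** **1. Who is left out.** The sections combine as follows.

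| Question | Rule for PK (5.7.3 with 5.2.2) | Safety set (5.2.3) |
|---|---|---|
| Entry condition | Part 3 off-state score at baseline and Week 12 | At least one dose |
| Grouping | As randomised | As actually treated |
| Dosed and sampled, no Week 12 score | Out of the tables at every visit | In |

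**2. How many.** The inputs are from sections 4.1 and 4.4: about 120 randomised, 60 per arm, about 108 evaluable.

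- Implied loss: 1 − 108/120 = 0.10. The SAP does not state this 10%; it follows from the two figures.
- Reproducing the plan's number: 108 / (1 − 0.10) = 120.
- Subjects outside the mITT set: 120 − 108 = 12, or 12/2 = 6 per arm if balanced.

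The split by arm is unknown, so the share of active subjects missing from the PK tables could be:

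| Active subjects excluded | Share of 60 |
|---|---|
| 0 | 0% |
| 3 | 5% |
| 6 (balanced) | 10% |
| 9 | 15% |
| 12 | 20% |

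These are upper bounds, because some of the 12 may never have been dosed or sampled. A dosed-subject set would raise the number in the PK summaries from about 108 to at most about 120.

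**3. Which visits.** Concentrations are summarised visit by visit. A subject who has stopped the drug gives no on-drug sample afterwards. For such subjects, the gap between the mITT summary and a dosed-subject summary is confined to visits before stopping and is about nil by Week 12. Subjects still on drug who lack only the rating could be missing at any visit.

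**4. Analytes.** The endpoint in section 5.7.3 covers the parent drug and the metabolites, 5.7.3.1 measures three analytes, and its summary sentence names one. These do not match.

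**5. Week 14.** Section 5.7.3.1 gives the Week 14 sample two descriptions: pre-dose, and final follow-up. Section 4.8 shows no study agent administration at Visit 7, and its note 5 lists no pre-dose draw there. The passages conflict and must be reconciled.

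**The case against.** Several points on the other side stand.

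- **Listings.** A reader might infer that early stoppers' concentrations go unreported. The SAP does not support that. Section 5.1 and item 5 of Appendix A say that listings in general include all randomised subjects, and section 5.1 adds that they hold all data collected. The loss is from the summary tables.
- **Metabolites.** A reader might infer a decision to omit them. Section 5.7.3 names them among the endpoints in scope and promises descriptive statistics. The table shells are in separate files (section 1) and were not available here. This is an inconsistency between two sections, not a documented omission.
- **Completers.** The mITT set is not the set of treatment completers. A subject who stops the drug but has a Week 12 score stays in. Section 4.7 asks sites to attempt the end-of-treatment assessments at early termination, and the SAP does not say whether these count as Week 12.
- **Size of bias.** It is tempting to assume that excluded subjects had higher exposure. With 10% excluded at m times the completers' exposure, the completer mean relative to all dosed subjects is 1/(0.9 + 0.1m). That is 4.8%, 9.1% and 16.7% too low at m = 1.5, 2 and 3. The SAP gives no basis for any m. Missed doses would push the other way, missing scores may reflect COVID-19 rather than tolerability, and the formula needs every excluded subject to have an on-drug sample at that visit.
- **Misallocation.** This is hypothetical; nothing in the SAP suggests that it occurred.
- **Consequence.** PK is exploratory and descriptive, and no hypothesis test in the SAP depends on it.

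These points limit the reach of the concern. They do not explain why a Week 12 motor score should govern entry to a plasma concentration table, and they do not remove the two wording conflicts in 5.7.3.1.

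**Conclusion.** The point holds in a limited form. As written, the plan removes dosed subjects with valid samples from the PK summary tables when they lack a baseline or Week 12 off-state Part 3 score, and it groups the rest as randomised. On the plan's own figures this is at most about 12 subjects, or 0 to 12 of the 60 active, with 6 as the balanced case. That rests on the evaluable target being met and on those subjects having been dosed and sampled. The direction and size of any effect on mean concentrations cannot be derived from the SAP, and the effect would fall mainly on earlier visits.

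Separately, 5.7.3.1 is inconsistent with 5.7.3 on analytes and with section 4.8 on the Week 14 sample. The priority is low: worth correcting, with no bearing on the primary or secondary efficacy results.

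**What to change.** Make three changes of wording:

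1. In section 5.7.3, add: 'PK concentrations will be summarised for Safety-population subjects with at least one evaluable plasma concentration obtained after the first dose, by treatment actually received.' The phrase 'after the first dose' matters because Weeks 2 and 8 have only a sample drawn before that visit's dose, and several of the later timed samples are optional (section 4.8, note 5). A requirement for a sample after the same visit's dose could exclude valid subjects.
2. In section 5.7.3.1, replace the summary sentence with: 'Concentrations of AKST4290, M227 and M373 will be summarised descriptively at each visit timepoint.'
3. Reconcile the description of the Week 14 sample in section 5.7.3.1 with section 4.8 and its note 5.

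The cost is SAP wording, a different population flag in the PK tables, and metabolite rows if the shells lack them. No new data are needed. Changing the efficacy population would not make this edit for PK, because an ITT set would still group subjects as randomised.
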